Protocol Title: SSRI Effects on Depression and Immunity in HIV/AIDS

NCT Number: NCT02620150

Document: Statistical Analysis Plan

Document Date: March 10, 2015

C.3 Research Design and Methods

Aim 1 Determine the effects of an SSRI on innate immunity and inflammation in depressed HIV seropositive individuals.

C.3.1 Summary

This will be the first placebo-controlled RCT to determine the immunomodulatory effects of SSRI therapy among a contemporary, urban cohort of HIV-seropositive individuals whose viral load is well controlled, yet still experiences immune dysregulation due to co-morbid depression and HIV infection. Comparing the two depressed groups that are randomly assigned to receive SSRI or placebo will allow us to address novel aims: can SSRI treatment and improvement of depression reverse the immune dysregulation of depression and HIV. Comprehensive biomarkers of innate immunity, and inflammation will be assayed via blood draw at baseline and at 2, 4, and 10 weeks. Additionally, we will monitor adherence to SSRI and antiretroviral medications in all participants using contemporary methodology (i.e., self-reported doses taken and missed, medication electronic monitoring system (MEMS) caps, and, for HIV, plasma viral load).

Aim 1A. Determine whether an SSRI upregulates innate immunity in depressed HIV seropositive individuals.

Hypothesis: SSRI is superior to placebo in restoring biomarkers of innate immune suppression (LUNK and intracellular IFNy in NK cells).

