C.5 Missing Data and Nonadherence For the primary analyses described above, premature discontinuation from treatment and occasional missing weekly appointments will lead to incomplete data. The mixed effects models for Aim 1, Hypothesis 1 described above can make use of all available data provided by subjects, but the inferences drawn from them will be unaffected by the missing data only if the missing data can be regarded as ignorable. For the other primary responses, dropouts will not provide any responses, so the basic models require ignorable dropout. To assess the sensitivity of our analyses to this assumption, we will also use selection models (143) to examine the effects of missing data: we will explicitly model the probability of premature discontinuation at a time point as a function of baseline characteristics and responses at previous time points, using a logistic regression model. For the longitudinal analyses of Aim 1, Hypothesis 1, these probabilities will provide time varying (inverse) weights for reruns of the primary analysis. For the other primary hypotheses, the overall probability of dropout will be used as a weight, and incorporated into a weighted analysis of these hypotheses. We will perform these analyses in a range of assumptions on the dropout process and assess the sensitivity of results to them. To account for possible non-adherence to assigned intervention, we will use self-report of pill ingestion and MEMS caps, as well as RNA viral load for cART. We will use the methods of Nagelkerke et al (144, 145), to obtain estimates of the intervention effect in a population compliant with treatment i.e. the Complier Average Causal Effect (CACE).

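### SAP C.5 does not match the mixed-model plan for the four primary markers, gives a dropout weight that is not valid as written, and specifies no non-ignorable scenario

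*SAP*

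**What the plan says.** SAP C.3.1 states that "biomarkers of innate immunity, and inflammation will be assayed via blood draw at baseline and at 2, 4, and 10 weeks". SAP C.3.2.a, and the analysis plan for the primary aims in the protocol's Accrual section, apply linear mixed effects models to the innate immunity markers (LUNK, intracellular IFN-gamma) and the inflammation markers (IL-6, CRP) alike.

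SAP C.5 then divides the primary analyses in two:

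- **First group.** "The mixed effects models for Aim 1, Hypothesis 1 described above can make use of all available data provided by subjects". For this group, "these probabilities will provide time varying (inverse) weights for reruns of the primary analysis".
- **Second group.** "For the other primary responses, dropouts will not provide any responses, so the basic models require ignorable dropout". For this group, "For the other primary hypotheses, the overall probability of dropout will be used as a weight".

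On the ignorability assumption C.5 says: "To assess the sensitivity of our analyses to this assumption, we will also use selection models". The model it describes is a logistic regression for the "probability of premature discontinuation at a time point as a function of baseline characteristics and responses at previous time points". It adds: "We will perform these analyses in a range of assumptions on the dropout process". It gives no parameter, no range and no term for an unseen value.

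**The concern.** Three things do not fit.

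1. No primary marker belongs in C.5's second group. All four have post-baseline draws and all four go into a mixed model. The label Aim 1, Hypothesis 1 is not defined either: Aims 1A and 1B each carry one unnumbered hypothesis. A programmer cannot tell which markers get which treatment.
2. The second group's weight is a probability of leaving. Weighting that corrects for dropout uses the inverse of the probability of remaining.
3. The check is meant to show whether results depend on ignorability, but the one model written out conditions only on observed data. Agreement between that rerun and the primary model is no evidence about dropout that depends on unseen values.

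The stake is the credibility of the sensitivity analysis. A faulty weight can make a sound primary result look unstable, and a check confined to observed data can reassure where it should not. Unequal dropout is foreseeable, because the protocol's Treatment section withdraws and replaces subjects who do not tolerate study drug. Whether dropout depends on unseen marker values is unknown.

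**Working it through.** **1. The plan's own figure.** Inputs from the protocol's power paragraph and SAP C.3.2.b: two-sided alpha 0.025, 80% power, within-person correlation 0.6, 10% attrition. With 180 subjects in two equal arms, 90 x 0.9 = 81 per arm remain. The variance of a mean of three equally correlated visits is (1 + 2 x 0.6)/3 = 0.7333. The standard error of the difference is sqrt(2 x 0.7333/81) = 0.135. The detectable effect is (2.241 + 0.842) x 0.1346 = 0.415, against 0.41 in the protocol (0.4 in the SAP). The SE implied by the protocol's figure is 0.41/3.083 = 0.133, used below as the yardstick.

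**2. Do dropouts provide data?** Expected dropouts: 10% of 180 = 18. If they are spread evenly over the three intervals between draws, 18 x 2/3 = 12 have at least one post-baseline sample. If spread evenly by week, 18 x 0.8 = 14.4. So about 12 to 14 of 18 provide responses on every marker.

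**3. The weights.** Take two completers with dropout probabilities p = 0.05 and 0.30.

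| Weight | p = 0.05 | p = 0.30 | Ratio |
|---|---|---|---|
| 1/(1-p), inverse probability of remaining | 1.05 | 1.43 | 1.36 |
| p, as written for the second group | 0.05 | 0.30 | 6 |
| 1/p, inverting the discontinuation probability | 20 | 3.3 | 0.17 |

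Using p over-weights completers who resemble dropouts. Using 1/p reverses the direction.

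**4. Dropout driven by observed values.** Large simulated samples (300,000 or more per arm), four visits, correlation 0.6, true effect 0.41 at weeks 2, 4 and 10, 10% dropout per arm. Active-arm dropout depends on the last observed value at log-odds -1 or +1 per SD; placebo dropout is random. These mechanisms are assumptions. The contrast is the mean of the three post-baseline differences.

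| Analysis | Dropout model | -1 | +1 |
|---|---|---|---|
| Mixed model | none needed | 0.41 | 0.41 |
| Inverse probability of remaining | with arm and arm-by-response | 0.41 | 0.41 |
| Inverse probability of remaining | C.5's listed predictors only | about 0.45 | about 0.37 |
| Probability of dropout | with arm and arm-by-response | about -0.09 | about 0.91 |
| Probability of dropout | C.5's listed predictors only | about 0.50 | about 0.32 |

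Without arm terms the dependence is averaged over the arms, so the active arm is under-corrected and placebo is corrected for a dependence it does not have.

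**5. Purely random dropout, 90 per arm.** With arm terms, the literal weight has SD 0.315 against 0.131 for the mixed model, and differs from it by more than one SE (0.133) in 66% of simulated trials. With the listed predictors only, its SD is 0.136 against 0.132 for unweighted completers, and it moves more than 0.133 from them in 1% of trials.

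**6. Dropout driven by unseen active-arm values** (log-odds +1 or -1 per SD). At 10% per arm the mixed model gives 0.384 or 0.436. At an assumed 15% active and 5% placebo it gives 0.370 or 0.450. The bias is 0.41 - 0.384 = 0.026 to 0.41 - 0.370 = 0.040, that is 0.026/0.133 = 0.2 to 0.040/0.133 = 0.3 SE. Inverse weighting with arm terms agrees with the mixed model within 0.002, so it shares the bias.

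**The case against.** The case for C.5 has four parts.

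- **It does not rule out non-ignorable models.** A reader might infer that the check covers only dropout explained by observed data. The documents do not support that: C.5 names selection models and promises a range of assumptions, and the textbook it cites cannot be consulted here. What stands is that no non-ignorable scenario is specified.
- **The weight may be shorthand.** The preceding sentence says inverse weights for the first group. But the quantities to be inverted there are probabilities of discontinuation, and step 3 shows that inverting those is also wrong. The text needs correcting on either reading.
- **The striking figures need arm in the dropout model.** A reader might infer that C.5 by itself yields -0.09 or 0.91, or unstable reruns in 66% of trials. C.5 does not name arm among its predictors, although arm could be read into baseline characteristics. Without it the distortion is about 0.09 SD in either direction. Nor do the rerun and the mixed model then always agree: for unseen-value dropout (+1, 15%/5%) they give 0.329 and 0.369.
- **The effect is small and secondary.** A reader might infer that the primary result is compromised. It is not: C.3.2.a defines the primary analysis and is untouched, and the bias in step 6 is modest. The 15%/5% split has no source in the documents.

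Weighting on observed data is still worth keeping, because it can correct for baseline covariates that the primary model omits.

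**Conclusion.** The concern holds in a limited form. The conflict between C.5 and C.3.1, C.3.2.a and the protocol follows from the text alone. So does the finding that neither p nor 1/p is a valid dropout weight, and that the promised test of ignorability has no specified non-ignorable scenario.

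The size depends on assumed mechanisms. For observed-value dropout in the active arm at log-odds of 1 per SD, the literal weight is off by about 0.09 SD with the listed predictors and about 0.5 SD with arm terms. Properly inverted weights from the listed predictors alone are still off by about 0.04 SD. Non-ignorable dropout in the active arm biases the mixed model by about 0.03 to 0.04 SD, and a valid weighted rerun would not reveal it. The damage is confined to the sensitivity analysis. This should be fixed before analysis, but it does not threaten the primary model or the sample size.

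**What to change.** In SAP C.5:

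1. State that the mixed model using all available data applies to LUNK, intracellular IFN-gamma, IL-6 and CRP.
2. Delete the two sentences on the other primary responses and the other primary hypotheses, and replace the undefined hypothesis label.
3. Define the weights for all four markers as the inverse cumulative probability of remaining, from a dropout model that includes treatment arm and its interaction with previous responses.
4. Describe that rerun as a check under dropout explained by observed data.
5. Replace the open-ended range of assumptions with one pre-specified non-ignorable sensitivity analysis, for example a delta-adjusted or pattern-mixture analysis varied by arm to the tipping point, over a range the sponsor justifies.

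The cost is SAP wording and modest programming. No new data are needed.
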